1. INTRODUCTION

Dietary fibres have long been recognized for their important role in a healthy diet due to their negative association with, and even management of, chronic diseases such as obesity, diabetes, metabolic syndrome, cardiovascular disease and inflammatory-bowel disease among others (1–3). Emerging evidence has suggested that these benefits could largely be attributed to short chain fatty acids (SCFA) (acetate, propionate and butyrate), the main by-products of fibre fermentation in the gut (1,4). Our research group has demonstrated that a long-term elevation in the SCFA propionate significantly reduced body weight gain in overweight adults and reduced liver fat storage (5).

The current project will examine potential mechanisms for the positive effect of propionate on energy homeostasis and metabolic profile. We will examine the effects of propionate on circulating glucose, insulin and lipid levels at rest, following moderate-intensity exercise and mixed meal tolerance test.

To acutely increase propionate absorption from the gut the present project will use a simple nutritional supplement: sodium propionate in a hydroxypropylmethyl cellulose (HPMC) capsule. This capsule is coated with an enteric film which prevents gastric digestion until the capsule reaches the intestine. This nutritional supplement has been used in human volunteers in a previously approved ethics application (12/LO/1769: Oral propionate and glucose homeostasis). A 5g acute dose of sodium propionate had previously been tested and reported no adverse effects (6) . The MHRA have confirmed that encapsulated sodium propionate is not classed as an investigative medicinal product (correspondence attached with application).

STUDY: The acute effects of short chain fatty acids on energy homeostasis

Obesity is a major global health concern where it has more than doubled since 1980 inflicting around 13% of the population world-wide(7). In England alone, more than half of the population is either overweight or obese (8). Causes of obesity are mainly environmental where excess dietary intake and physical inactivity play a major role (9). Obesity increases the risk of various chronic diseases such as type 2 diabetes, hypertension, dyslipidaemia and cardiovascular disease which place a significant economic burden on health care systems (9,10). And these diseases often develop as a consequence of the metabolic changes that occur with obesity such as disturbances in glucose homeostasis, insulin sensitivity and lipid profile (11,12). Thus, efforts have been directed to address these metabolic abnormalities and environmental causes to help alleviate obesity and its adverse outcomes.

Short chain fatty acids, acetate, propionate and butyrate, have shown to exert multiple physiological changes that are beneficial in obese states. Propionate, in particular, has shown to exert multiple physiological benefits. For instance, it seems to regulate hepatic lipid metabolism through a reduction in intrahepatic triglyceride concentration (5). It can also enhance the lipid buffering capacity of adipose tissue through an increase in lipoprotein lipase activity and consequently, can decrease serum free fatty acids (13). Moreover, it can increase energy expenditure via diet-induced-thermogenesis through activation of the sympathetic nervous system (14), and can reduce energy intake through its effect on appetite hormones and decrease long-term weight gain and fat accretion in overweight adults (5). As for glucose metabolism, propionate serves as a gluconeogenic

substrate (15–17) and can thus spare/preserve the use of amino acids for gluconeogenesis (18,19). Moreover, it seems to hold promising results in enhancing hepatic and peripheral insulin sensitivity(20) and overall glucose homeostasis (20,21).

An intervention which elevates propionate release from the gut may therefore protect against obesity and its associated metabolic disruptions through enhanced glucose tolerance, lipid profile, and increased energy expenditure. Thus, the aim of this project is to investigate the acute effects of gut-derived propionate on the regulation of energy expenditure, substrate oxidation and overall metabolic profile in humans throughout different physiological states (fasting, postprandial and during physical activity). This study is an extrapolation based on a previously ethically approved research study (15/WA/0415) which demonstrated an increase in energy expenditure, lipid oxidation rates and circulating levels of propionate following an acute dose of 5 g sodium propionate supplemented over a 180 min time period. As can be seen from the below graphs, circulating levels of propionate increased over time to reach a peak at 180 min and thus for this study we would want to determine the trend in propionate levels over a longer period (300 minutes) while also examining energy expenditure and lipid oxidation with a properly matched energy control.

[figure not shown]

Figure 1. The effect of oral propionate supplementation on short chain fatty acid levels in peripheral blood. A. Propionate (Time×Trial: $P= 0.043$) and B. propionate iAUC ($P=0.021$).

[figure not shown]

Figure 2. The effect of oral propionate supplementation on resting energy expenditure and substrate oxidation. A. Resting energy expenditure (TimexTrial: $P= 0.388$) and **B.** resting energy expenditure iAUC ($P=0.036$). **C.** Lipid oxidation (TimexTrial: $P= 0.075$) and **D.** lipid oxidation iAUC ($P=0.019$).

2. Study 1: The acute effects of propionate on energy metabolism during fasting.

Study methodology: A randomized, placebo controlled, double blind, cross-over study.

Participants: 40 healthy male and female volunteers aged between 18 and 65 years with body mass index (BMI) of 18-35 kg/m².

Support of number of volunteers: A power calculation confirmed that 34 participants would be sufficient to detect a 5% difference in the primary outcome, resting energy expenditure, with a standard deviation (SD) of 10 %($\alpha=0.05$, power=0.80). 40 participants were recruited to allow a dropout rate of 15%.

Recruitment

Volunteers will be recruited via email using a healthy volunteer database of the NIHR/Wellcome Trust Imperial Clinical Research Facility (CRF) or via a study advertisement. Interested volunteers will be asked to fill in a pre-screening questionnaire and if deemed eligible will be invited for a screening visit at the CRF in Hammersmith Hospital.

Visit 1- Health Screening

Participants will attend the NIHR/Wellcome Trust Imperial Clinical Research Facility at Hammersmith Hospital where their eligibility will be assessed via an interview which discusses medical history, family history of medical illness and drug history. They will have a blood test (Full blood count liver function test, urea & electrolytes and lipids) and height and weight measurements will also be taken. They will also have an electrocardiogram (ECG) and blood pressure will be recorded. All women of child bearing age will have a pregnancy test. These results will be examined and approved by a qualified research doctor before the volunteers will be formally enrolled in the study.

Visits 2,3,4– Study Visits

Subjects will be asked to complete three study visits that will last approximately 6 hours each. The three study visits will need to be separated by a period of at least 3 days. Participants will be told not to start any other new diets or intensive exercise regimes during the study period as this may give us conflicting results.

In a randomized order, volunteers will complete the following three study visits:

1. Sodium Chloride (Sodium Control)
2. Palmitic Acid (Fatty Acid Control)
3. Sodium Propionate

[figure not shown]
The day prior to each study visit, participants will be requested to refrain from strenuous exercise, caffeine and alcohol. Participants will then be requested to fast overnight (they are allowed to drink water) and will come to the NIHR/Wellcome Trust Imperial Clinical Research Facility at Hammersmith Hospital the following morning. Fasting blood samples will be taken through an intravenous peripheral cannula at -15 and 0 min.

Between the fasting blood samples, resting energy expenditure will be measured with a standard indirect calorimeter. The calorimeter captures expired air from a large, transparent canopy, worn over the head and thorax, and is typically very well tolerated. Each participant will be asked to lie in a semi-recumbent position under the canopy. Measurements will be taken for 20 min in order to assess the participants' resting metabolic rate (RMR) and respiratory quotient (RQ). Additional measures of RMR and RQ will be recorded at 40-60 min, 100-120 min, 160-180, 220-240 min and 280-300.

Following the 0 min sample volunteers will ingest a capsule containing either 1g sodium propionate (Propionate) or 1 g sodium chloride (Sodium Control) or 1g palmitic acid (fatty acid control) at 30, 60, 90 and 120 (5g in total)

Blood samples will be taken at 30, 60, 90, 120, 150, 180, 210, 240 and 300 min to measure hormones and metabolites. 110 ml (11 × 10 ml) will be collected throughout each study visit. Blood pressure and heart rate will be measured at baseline and every hour at 60, 120, 180, 240 and 300 min. Urine will be collected throughout the study visit to measure urea concentrations for calculation of protein oxidation rates. Subjects will empty their bladder before baseline blood samples and collect all urine thereafter for a period of 300 min using appropriate measurement containers.

Figure 1: Study visit protocol for study 1.

3. Study 2: The acute effects of propionate on energy metabolism during exercise.

Study methodology: A randomized, placebo controlled, double blind, cross-over study.

Participants: 40 healthy male and female volunteers aged between 18 and 65 years with body mass index (BMI) of 18-35 kg/m².

Support of number of volunteers: A power calculation confirmed that 34 participants would be sufficient to detect a 5% difference in the primary outcome, resting energy expenditure, with a standard deviation (SD) of 10 % ($\alpha=0.05$, power=0.80). 40 participants were recruited to allow a dropout rate of 15%.

Recruitment

Volunteers will be recruited via email using a healthy volunteer database of the NIHR/Wellcome Trust Imperial Clinical Research Facility (CRF) or via a study advertisement. Interested volunteers will be asked to fill in a pre-screening questionnaire and if deemed eligible will be invited for a screening visit at the CRF in Hammersmith Hospital.

Visit 1- Health Screening

Participants will attend the NIHR/Wellcome Trust Imperial Clinical Research Facility at Hammersmith Hospital where their eligibility will be assessed via an interview which discusses medical history, family history of medical illness and drug history. They will have a blood test (Full blood count liver function test, urea & electrolytes and lipids) and height and weight measurements will also be taken. They will also have an electrocardiogram (ECG) and blood pressure will be recorded. All women of child bearing age will have a pregnancy test. These results will be examined and approved by a qualified research doctor before the volunteers will be formally enrolled in the study.

Visit 2 – Maximal Exercise Test

Subjects will come to the NIHR/Wellcome Trust Imperial Clinical Research Facility at Hammersmith Hospital and perform an incremental exercise test to volitional exhaustion on a cycle ergometer. Volunteers will start cycling at 50 Watts (W) and the workload will increase in 25 W increments every 3 min until voluntary exhaustion. This will determine maximal oxygen uptake ($VO_{2\max}$), maximal aerobic power output (W_{\max}) and maximal heart rate (HR_{\max}). Non-invasive measures of respiratory exchange and heart rate will be recorded throughout the test. The maximal exercise test is a common measurement in exercise physiology research and presents no greater risk than the exercise activities normally undertaken by the recruited volunteers. The visit would last approximately 1 hour.

Visits 3,4,5 – Study Visits

Subjects will be asked to complete three study visits that will last approximately 6 hours each. The three study visits will need to be separated by a period of at least 3 days. Participants will be told not to start any other new diets or intensive exercise regimes during the study period as this may give us conflicting results.

In a randomized order, volunteers will complete the following three study visits:

1. Sodium Chloride (Sodium Control)
2. Palmitic Acid (Fatty Acid Control)
3. Sodium Propionate

[figure not shown]
The day prior to each study visit, participants will be requested to refrain from strenuous exercise, caffeine and alcohol. Participants will then be requested to fast overnight (they are allowed to drink water) and will come to the NIHR/Wellcome Trust Imperial Clinical Research Facility at Hammersmith Hospital the following morning. Fasting blood samples will be taken through an intravenous peripheral cannula at -15 and 0 min.

Between the fasting blood samples, resting energy expenditure will be measured with a standard indirect calorimeter. The calorimeter captures expired air from a large, transparent canopy, worn over the head and thorax, and is typically very well tolerated. Each participant will be asked to lie in a semi-recumbent position under the canopy. Measurements will be taken for 20 min in order to assess the participants' resting metabolic rate (RMR) and respiratory quotient (RQ). Additional measures of RMR and RQ will be recorded at 40-60 min, 100-120 min, 160-180 220-240 min and 280-300.

Following the 0 min sample volunteers will ingest a capsule containing either 1g sodium propionate (Propionate) or 1 g sodium chloride (Sodium Control) or 1g palmitic acid (fatty acid control) at 30, 60, 90 and 120 (5g in total)

At 180 min, volunteers will have their heart rate recorded while they complete 60 min of constant-load cycling at a workload corresponding to 40% Wmax, determined from Visit 2 whilst breathing through a mouthpiece connected to an indirect calorimeter to determine energy expenditure and substrate oxidation rates during exercise. Blood samples will be taken at 30, 60, 90, 120, 150, 180, 210, 240 and 300 min to measure hormones and metabolites. 110 ml (11 × 10 ml) will be collected throughout each study visit. Blood pressure and heart rate will be measured at baseline and every hour at 60, 120, 180, 240 and 300 min. Urine will be collected throughout the study visit to measure urea concentrations for calculation of protein oxidation rates. Subjects will empty their bladder before baseline blood samples and collect all urine thereafter for a period of 300 min using appropriate measurement containers.

Figure 2: Study visit protocol for study 2.

4. Study 3: The acute effects of propionate on postprandial metabolism:

Study methodology: A randomized, placebo controlled, double blind, cross-over study.

Participants: 40 healthy male and female volunteers aged between 18 and 65 years with body mass index (BMI) of 18-35 kg/m².

Support of number of volunteers: A power calculation confirmed that 34 participants would be sufficient to detect a 5% difference in the primary outcome, resting energy expenditure, with a standard deviation (SD) of 10 % ($\alpha=0.05$, power=0.80). 40 participants were recruited to allow a dropout rate of 15%..

Recruitment

Volunteers will be recruited via email using a healthy volunteer database of the NIHR/Wellcome Trust Imperial Clinical Research Facility (CRF) or via a study advertisement. Interested volunteers will be asked to fill in a pre-screening questionnaire and if deemed eligible will be invited for a screening visit at the CRF in Hammersmith Hospital.

Visit 1- Health Screening

Participants will attend the NIHR/Wellcome Trust Imperial Clinical Research Facility at Hammersmith Hospital where their eligibility will be assessed via an interview which discusses medical history, family history of medical illness and drug history. They will have a blood test (Full blood count liver function test, urea & electrolytes and lipids) and height and weight measurements will also be taken. They will also have an electrocardiogram (ECG) and blood pressure will be recorded. All women of child bearing age will have a pregnancy test. These results will be examined and approved by a qualified research doctor before the volunteers will be formally enrolled in the study.

Visits 2,3,4 – Study Visits

Subjects will be asked to complete four study visits that will last approximately 6 hours each. The three study visits will need to be separated by a period of at least 3 days. Participants will be told not to start any other new diets or intensive exercise regimes during the study period as this may give us conflicting results.

In a randomized order, volunteers will complete the following four study visits:

1. Sodium Chloride (Sodium Control)
2. Palmitic Acid (Fatty Acid Control)
3. Sodium Propionate

[figure not shown]
The day prior to each study visit, participants will be requested to refrain from strenuous exercise, caffeine and alcohol. Participants will then be requested to fast overnight (they are allowed to drink water) and will come to the NIHR/Wellcome Trust Imperial Clinical Research Facility at Hammersmith Hospital the following morning. Fasting blood samples will be taken through an intravenous peripheral cannula at -15 and 0 min.

Between the fasting blood samples, resting energy expenditure will be measured with a standard indirect calorimeter. The calorimeter captures expired air from a large, transparent canopy, worn over the head and thorax, and is typically very well tolerated. Each participant will be asked to lie in a semi-recumbent position under the canopy. Measurements will be taken for 15 min in order to assess the participants' resting metabolic rate (RMR) and respiratory quotient (RQ). Additional measures of RMR and RQ will be recorded at 40-60 min, 100-120 min, 160-180, 220-240 min and 280-300.

Following the 0 min sample volunteers will ingest a capsule containing either 1g sodium propionate (Propionate) or 1 g sodium chloride (Sodium Control) or 1g palmitic acid (fatty acid control) at 30, 60, 90 and 120 (5g in total)

At 180 min participants will have mixed meal tolerance test in the form of an ensure drink (500 kcal). Blood samples will be taken at 30, 60, 90, 120, 150, 180, 195, 210, 240 and 300 min to measure hormones and metabolites. 120 ml (12 x 10 ml) will be collected throughout each study visit. Blood pressure and heart rate will be measured at baseline and every hour at 60, 120, 180, 240 and 300 min.

Urine will be collected throughout the study visit to measure urea concentrations for calculation of protein oxidation rates. Subjects will empty their bladder before baseline blood samples and collect all urine thereafter for a period of 300 min using appropriate measurement containers.

Figure 3: Study visit protocol for study 3.

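### The introduction promises an energy-matched control, but the arms are matched on mass only, so neither control is energy-matched by content (minor)

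*Combined protocol and SAP*

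**What the plan says.** The introduction cites an earlier study that "demonstrated an increase in energy expenditure, lipid oxidation rates and circulating levels of propionate following an acute dose of 5 g sodium propionate". It gives two reasons for going further: following propionate levels for longer (300 minutes), and "while also examining energy expenditure and lipid oxidation with a properly matched energy control". It does not say which control is meant.

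The Study Visits text of Study 1 (section 2) sets each dose as "1g sodium propionate (Propionate) or 1 g sodium chloride (Sodium Control) or 1g palmitic acid (fatty acid control"), 5 g in total. Sections 3 and 4 repeat this for Studies 2 and 3. The arm lists name the two controls by role: a sodium control, and "Palmitic Acid (Fatty Acid Control").

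No section gives an energy value for any arm, a matching calculation, a different palmitic acid dose, or an absorption argument. Resting energy expenditure is the primary outcome in the sample size paragraph of each study.

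**The concern.** A control matched on energy would let a reader separate an effect of propionate from the effect of taking in some energy. The introduction ties that property to energy expenditure, the primary outcome, and to lipid oxidation. Equal mass does not deliver it when the substances differ in energy per gram.

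What is at stake is interpretation. Propionate carries energy that sodium chloride does not, so a rise in energy expenditure over sodium chloride alone does not exclude energy load. Palmitic acid carries more energy by content than propionate, and it is itself a fat, which may affect the lipid oxidation contrast. A report that repeated the introduction's wording would describe a contrast as energy-matched when the design does not make it so.

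**Working it through.** **The plan's own figure.** The plan states no energy figure, so only the sample size can be reproduced. Take a paired t test, two-sided α = 0.05, power 0.80, a 5% difference, and the 10% SD read as the SD of within-person differences. This gives n = 33.4, so 34, with power 0.808 at n = 34. Then 34/0.85 = 40. Both stated figures reproduce, and neither depends on the energy content of the capsules.

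**Energy by content.** Inputs from the protocol: 5 g of each substance. Inputs from chemical formulas: sodium propionate C3H5O2Na, 96.06 g/mol, 3.5 mol O2 per mol for full oxidation; palmitic acid C16H32O2, 256.43 g/mol, 23 mol O2 per mol; sodium chloride has nothing to oxidise. Assumption: energy is proportional to O2 demand, at 430–460 kJ per mol O2 (4.184 kJ per kcal).

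- Sodium propionate: 3.5/96.06 = 36.4 mmol O2 per g.
- Palmitic acid: 23/256.43 = 89.7 mmol O2 per g.
- Ratio: 89.7/36.4 = 2.46. Inverse: 0.406.
- If the energy per mol O2 differs between the two substances within 430–450 kJ, the ratio runs from 2.46 × 430/450 = 2.35 to 2.46 × 450/430 = 2.58. It does not approach 1.

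| 5 g of | kcal by content |
|---|---|
| Sodium chloride | 0 |
| Sodium propionate | 18.7–20.0 |
| Palmitic acid | 46.1–49.3 |

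The gap between palmitic acid and propionate is 27.4–29.3 kcal. The dosing text lists four times after baseline but a 5 g total, which implies a fifth dose at 0 min. The ratio is the same for 4 g or 5 g.

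**Absorption.** If palmitic acid is absorbed at 80%, 60% or 40% relative to propionate, the absorbed energy ratio is 1.97, 1.48 or 0.98. Equality needs 1/2.46, about 41%.

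**Direct bias on resting energy expenditure, Study 1 only.** Further assumptions, none from the documents: a thermic effect of 3–10% of absorbed energy, and resting expenditure of 1.0–1.4 kcal/min, which is 300–420 kcal over 300 min.

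- Palmitic acid contrast, common thermic effect, full absorption: 27.4 × 0.03 = 0.8 kcal over 420, to 29.3 × 0.10 = 2.9 kcal over 300. That is 0.2–1.0%, against a propionate effect.
- Same, 60% relative absorption: the gap is 8.9–9.6 kcal, so about 0.1–0.3%.
- Same, 40% relative absorption: the gap is about −0.3 kcal, so about zero.
- Unequal thermic effects, full absorption, palmitic acid at 3% and propionate at 10%: 1.4–1.5 against 1.9–2.0 kcal. The sign reverses, to about 0.1–0.2% in favour of propionate.
- The opposite extreme, palmitic acid at 10% and propionate at 3%: 4.6 − 0.6 = 4.0 kcal over 420, to 4.9 − 0.6 = 4.3 kcal over 300. That is 1.0–1.4% against propionate.
- Sodium chloride contrast: 18.7 × 0.03 = 0.6 kcal over 420, to 20.0 × 0.10 = 2.0 kcal over 300. That is 0.1–0.7% in favour of propionate.

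**Studies 2 and 3.** The content mismatch is the same, but the fasting figures do not carry over. Study 2 adds "60 min of constant-load cycling at a workload corresponding to 40% Wmax", and in Study 3 "At 180 min participants will have mixed meal tolerance test in the form of an ensure drink (500 kcal"). For scale, 27.4–29.3 kcal is 5.5–5.9% of that drink.

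**The case against.** The phrase appears once, in the introduction. The design sections never call a control energy-matched, and no section commits to an energy-matched conclusion. The bias on the primary outcome is small against the 5% target, and the sample size is untouched. All of this stands, and it sets the severity at minor. It does not remove the conflict: matching is stated as a reason for the study, and the dosing does not provide it.

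The missing absorption data also count. Poorly absorbed palmitic acid could supply about the same energy as propionate. That would need about 41% relative absorption, and the documents neither claim nor support it.

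Four stronger readings are tempting and should be resisted.

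- *Sodium chloride breaks the promise too.* It is labelled only a sodium control, so its zero energy breaks no promise of its own. By content, the two controls also bracket propionate, which has some interpretive value.
- *A rise over palmitic acid is conservative for energy load.* This follows for kilocalories absorbed above about 41%, but not necessarily for energy expenditure. Unequal thermic effects can reverse the sign.
- *The lipid oxidation contrast is biased by a stated percentage.* Calorimetry measures total oxidation, and ingested fat may replace the body's own fat. Any percentage depends on which substrate is displaced, which the documents do not say.
- *The energy expenditure result is invalid.* The figures above do not support that.

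**Conclusion.** The concern holds as an inconsistency between the introduction and the dosing text of all three studies. By content, palmitic acid, the only control that holds energy, has about 2.46 times the energy of the propionate dose, so neither control is energy-matched. This rests on chemical formulas and on energy being proportional to O2 demand.

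The direct bias on resting energy expenditure in Study 1 is about 0–1% with a common thermic effect. The upper end needs full absorption and a 10% thermic effect, and the direction is uncertain if the thermic effects differ. Absorption, thermic effect and resting expenditure are all assumed. No bias figure is given for lipid oxidation or for Studies 2 and 3. Severity: minor.

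**What to change.** In the introduction, replace the phrase about a matched energy control with *equal-mass sodium chloride and palmitic acid controls*, and draw no energy-matched conclusion from either contrast. Add three statements:

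1. A rise in energy expenditure over sodium chloride alone does not exclude energy load.
2. Palmitic acid supplies more energy by content, so a rise over it argues against energy load only if enough is absorbed (more than about 41% relative to propionate) and the thermic effects are similar.
3. Lipid oxidation against palmitic acid may be affected by the fat in that control. Give no percentage.

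This costs one phrase and three sentences. Sample size, visits and procedures stay as they are, and so does the power of each single contrast (about 0.81 for 34 paired participants).

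Optional, only if the capsules are not yet made and a content-matched control is wanted: fill about 0.41 g palmitic acid per 1 g sodium propionate, with inert filler to equal capsule weight. This needs a new capsule specification and a check that the blind holds. Incomplete absorption would then leave it below propionate in absorbed energy: about 15–16 kcal at 80% relative absorption and 11–12 kcal at 60%, against 19–20 kcal.

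### The primary comparison is not fixed: each study has two controls and five later REE windows but names no primary contrast or REE measure, and in Study 2 one resting window falls during exercise.

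*Combined protocol and SAP*

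**What the plan says.** REE is called the primary outcome only in the paragraph headed Support of number of volunteers, which is repeated almost unchanged in sections 2, 3 and 4 (Studies 1, 2 and 3): "A power calculation confirmed that 34 participants would be sufficient to detect a 5% difference in the primary outcome, resting energy expenditure". The paragraph adds an SD of 10%, alpha 0.05, power 0.80, and 40 recruited to cover 15% dropout.

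Each study gives every volunteer three conditions: sodium chloride, palmitic acid and sodium propionate. REE is measured at baseline and then in five windows. In Study 2 the schedule reads: "Additional measures of RMR and RQ will be recorded at 40-60 min, 100-120 min, 160-180 220-240 min and 280-300". In the same study volunteers, from 180 min, "complete 60 min of constant-load cycling at a workload corresponding to 40% Wmax". In Study 3 a 500 kcal drink is given at 180 min.

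The Introduction describes an earlier study "which demonstrated an increase in energy expenditure, lipid oxidation rates and circulating levels of propionate". Its legend for REE reports two analyses: Time x Trial, P=0.388, and incremental area under the curve (iAUC), P=0.036. The Introduction also says that the new work will look at energy expenditure against a control matched for energy, but it does not say which of the two controls this is or that it is the primary comparator. The supplied text has no statistical analysis section.

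**The concern.** One alpha and one 5% difference are stated, but the design offers two comparators and several ways to reduce six REE readings per visit to a test. Nothing says whether propionate must beat one named control, either control or both, or whether the test uses iAUC, mean change, a single window or a repeated-measures interaction. Left open, these choices can be made after the data are seen. The error rate is then no longer 5%, and the stated power belongs to no identified test.

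The schedule adds to this. A five-window summary would mix resting and exercise values in Study 2, and fasting and fed values in Study 3, although all three studies use the same power sentence for the same named outcome.

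**Working it through.** **Inputs.** From the plan: difference 5%, SD 10%, alpha 0.05, power 0.80, dropout 15%, two controls, five later windows. Assumed, because the plan does not give it: the correlation between the two within-person differences (propionate minus each control). It is 0.5 if the three conditions have equal variance, because the propionate visit is shared: covariance s², each variance 2s², ratio 0.5. Range examined: 0.2 to 0.8.

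**1. The plan's own figure.** Paired test on within-person differences:
- Normal approximation: ((1.960 + 0.842) x 10/5)² = 31.4, so 32.
- Exact noncentral t, two-sided: power 0.795 at n=33, 0.808 at n=34, 0.869 at n=40.
- Dropout: 34/0.85 = 40.

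So 34 and 40 are reproduced. A one-sided paired t-test would need 27, and a parallel two-group design 63 per arm. The figure therefore fits one two-sided paired contrast, with 10% as the SD of the within-person difference.

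**2. Either control may count, one REE measure, each at 0.05.**
- If the two tests were independent: 1 - 0.95² = 9.75%.
- Simulated paired t-tests, n=34, correlation 0.5: 9.1%. Over correlations 0.2 to 0.8: about 8% to 10%.

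A free choice of REE measure raises this further. The plan gives no correlation between measures from which to fix the amount.

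**3. Power under each rule that might be adopted (true difference 5%, correlation 0.5).**

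| Rule | n=34 | n=40 |
|---|---|---|
| One named contrast at 0.05 | 0.81 | 0.87 |
| Both controls must be beaten at 0.05 | 0.70 | 0.79 |
| Bonferroni (0.025 each), power for one given comparison | 0.71 | 0.79 |

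Under Bonferroni at n=34, the chance of at least one rejection is about 0.86 if the 5% effect exists against both controls, but about 0.72 if it exists against one only. For 0.80 on a given comparison, Bonferroni needs 41 evaluable; 41/0.85 = 48.2, so 49 recruited.

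**4. Windows against events.**
- Study 2: cycling runs from 180 to 180 + 60 = 240 min. The 220-240 min resting window lies wholly inside it.
- Study 3: the 220-240 and 280-300 min windows both come after the drink at 180 min.
- Study 1: neither event occurs, so all five windows are resting and fasting.

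REE over all five windows is therefore not resting energy expenditure in Study 2, and not fasting energy expenditure in Study 3.

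**The case against.** **The comparator is hinted at.** Of the two controls, palmitic acid supplies energy and sodium chloride does not, so the Introduction's remark on a control matched for energy points towards palmitic acid. This is fair, and it may be what the investigators intend. But it is rationale, it names neither control, and the power paragraph does not refer to it.

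**The physiological states differ by design.** The three studies are titled fasting, exercise and postprandial, so differences after 180 min are partly intended. This stands as an explanation of the schedule. It does not say which windows enter a primary outcome called resting energy expenditure.

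**Stronger readings that the documents do not support:**
- A reader might infer that the earlier study shows that the choice of analysis decides the result, or that its claim of an increase was wrong. Time x Trial asks whether the profiles differ in shape over time; iAUC asks about overall elevation. They are different hypotheses and can disagree without inconsistency, and the text does not say which was primary. The pair shows only that the choice of measure can matter.
- A reader might count two analyses against two controls and quote about 14% for any of four tests. The plan never says that Time x Trial will be used here, or that any one of four results may count, and the 14% also needs assumed correlations between windows.
- A reader might conclude that power falls short only if both controls must be beaten. Bonferroni also falls short at n=34 if the effect exists against one control only.
- Study 3 states: "In a randomized order, volunteers will complete the following four study visits". A reader might suspect a missing fourth condition. The visit heading there, the next mention of three visits, the three listed conditions and the reimbursement for Visits 2-4 all show a wording slip.

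**An analysis plan may exist elsewhere.** It could not be checked. If it does, citing it in the protocol would close most of the gap.

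**Conclusion.** The point holds as a gap in specification, not as a sample-size error. The 34 completers give power 0.81 for one paired contrast in one REE measure, and the text identifies neither. Its size, with one REE measure and either control allowed to count, is a type I error of about 9% instead of 5% (about 8% to 10% over the assumed correlations), and more if the measure is open too. The plan does not state an either-control rule; the figure is what follows if nothing rules it out. Power of 0.80 is not reached at 34 if both controls must be beaten (0.70), or under Bonferroni with an effect against one control only (about 0.72).

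The Study 2 overlap needs no assumption. The schedule as written places a resting reading of the primary outcome within the exercise period. Confidence in the point as a whole is medium, because an analysis plan outside the supplied text cannot be excluded.

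**What to change.** Before treatment codes are opened, for each study:

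1. Name one primary contrast (propionate against one stated control) and one REE summary measure, listing its windows.
2. Make the second control comparison and all other REE analyses secondary, or test them in a fixed sequence after the primary. With a fixed sequence over the two controls, the chance that both steps succeed is about 0.70 at n=34, so the second step should not be described as having 80% power.
3. State that power 0.80 with 34 completers applies to the named contrast only, and confirm that 10% is the SD of the within-person difference in that measure.
4. In Study 2, reconcile the 220-240 min resting window with the cycling period, so that no value recorded during exercise enters the primary resting measure. In Study 3, say whether windows after the drink belong to the primary measure.

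This costs about three sentences per study and no more participants; power stays at 0.81 for the named contrast. The downside is that a result seen only against the other control, or only in another REE analysis, cannot be the primary claim.
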